#### **7.7 Continued Access**

[figure not shown]
~~Patients who are still on study treatment at the time of study completion may continue to receive study treatment if they are experiencing clinical benefit and no undue risks.~~

~~The continued access period will apply to this study only if at least 1 patient is still on study treatment when study completion occurs. Lilly will notify investigators when the continued access period begins.~~

~~Patients who are in 30-day follow-up when the continued access period begins will continue in 30-day follow-up until the 30-day follow-up visit is completed.~~

~~The patient’s continued access will end when a criterion for discontinuation is met (Section 6.3). Continued access follow-up will begin the day after the patient and the investigator agree to discontinue study treatment and lasts 30 ( $\pm 3$ ) days.~~

~~Study procedures during continued access period are described in the Study Schedule (Continued Access) (Attachment 1).~~

a Lilly will notify sites when the study completion occurs and the continued access period begins.

b End of trial occurs at the last visit or last scheduled procedure for the last patient.

**Figure JJCC.3. Continued access diagram.**

### 8.1.2 Adverse Events

[...]

All AEs occurring after signing the ICF are recorded in the eCRF and assessed for serious criteria.

#### 8.1.2.2.2 On Study

[...]

This applies to the continued access period.

#### 8.1.2.2.3 Follow-Up Visit

[...]

This applies to the continued access follow-up in the continued access period.

## Attachment 1. Protocol JJCC Study Schedule

[...]

Continued Access

Cycle/Visit	Cycle n												30-day Follow-up Visitc
	Week 1			Week 2			Week 3			Week 4			
Day Relative to Day 1 in Each Cycle	1b	3	5	8	10	12	15	17	19	22	24	26	
LY3039478 therapy (dose)a	1	2	3	4	5	6	7	8	9	10	11	12	
CTCAE grading							X						X
Dispense/return LY3039478, diary/drug accountability	X												

Abbreviations: CTCAE = Common Terminology Criteria for Adverse Events

a LY3039478 is to be administered 3 times per week through each 28-day cycle.

b A delay in the start of a cycle due to holidays, weekends, bad weather, or other unforeseen circumstances will be permitted up to 3 working days.

c 30-day follow-up visit to occur 30 days ( $\pm 3$ ) after the patient and the investigator agree that the patient will no longer continue study treatment.

Note: Efficacy assessments will be done at the investigator's discretion based on the standard of care.

Assessment	Comments
CTCAE grading	Refer to Section 8.1.2 for reporting guidelines.
Dispense/return LY3039478, diary/drug accountability	Performed at the end of each cycle or the start of each cycle, and the end of study treatment.

Abbreviations: CTCAE = Common Terminology Criteria for Adverse Events.

### Generic Name (LY3039478) Indication studied

This Phase 1 study is a single center, nonrandomized, open-label, dose-escalation study of oral LY3039478 in Japanese patients with advanced and/or metastatic solid tumors.

Eli Lilly Japan K.K.  
[name]  
Protocol I6F-JE-JJCC  
Phase 1

Statistical Analysis Plan Version 1 electronically signed and approved by Lilly: 22 July 2016.

Statistical Analysis Plan Version 2 electronically signed and approved by Lilly: 26 April 2017.

Statistical Analysis Plan Version 3 electronically signed and approved by Lilly on date provided below.

Approval Date: 02-Apr-2019 GMT

### 3. Revision History

SAP Version 1 was approved prior to the first visit when a subject receives study drug or any other protocol intervention.

SAP Version 2 was approved prior to the data base lock. The main objective of this revision was to removed PET metabolic response analysis since the desired results cannot be obtained through programing. It was also updated to remove the summary table for tumor markers, the napoleon plot for the treatment duration, and the plot for the vital signs because it was determined that the listings are sufficient. The summary of laboratory parameters was also clarified, and the category for toxicity grade for overall adverse event summary table was modified from “grade 3 or 4” to “grade  $\geq 3$ ”.

SAP Version 3 was approved prior to the data base lock. It was updated to correct the categories of absolute QTcF value. Several other changes were made to clarify the definition.

## 4. Study Objectives

### 4.1. Primary Objective

The primary objective of this study is to evaluate the tolerability of LY3039478 up to the global recommended dose in Japanese patients with advanced solid tumors.

### 4.2. Secondary Objectives

The secondary objectives of this study are:

- to characterize the safety and toxicity profile of LY3039478,
- to evaluate the pharmacokinetic (PK) parameters of LY3039478
- to document any antitumor activity observed with LY3039478.

### 4.3. Exploratory Objectives

The exploratory objectives of this study are:

- to explore pharmacodynamic (PD) effects of LY3039478 on biomarkers indicative of Notch activity.
- to evaluate tumor tissue and blood for biomarkers related to solid tumors, the Notch signaling pathway and drug target pathways, immune functioning, and mechanism of action of study drug, and their potential association with the study objectives.
- to explore the utility of positron emission tomography (PET) scan to assess treatment effect with LY3039478.

## 5. Study Design

### 5.1. Summary of Study Design

Study JJCC is a Phase 1, single center, nonrandomized, single-arm, open-label, dose-escalation study of LY3039478 in Japanese patients with advanced solid tumors.

Study JJCC will consist of 2 dose levels, 25 and 50 mg LY3039478 TIW (3 or 6 patients per dose level). Transition of dose level (from 25 to 50 mg) will proceed if the frequency of dose-limiting toxicity (DLT) observed in Cycle 1 (28 days) is <33% of patients in the first dose level (25 mg). Figure JJCC.1 illustrates the study design.

Eligible patients will be treated with LY3039478 at the assigned dose. The planned duration of treatment is not fixed. Treatment will continue until disease progression, development of unacceptable toxicity, or any other discontinuation criteria are met (Figure JJCC.1).

[figure not shown]

Figure JJCC.1.

Illustration of study design.

### 5.2. Determination of Sample Size

The sample size will primarily be determined by the incidence of DLTs in patients in each dose level. Following a 3+3 dose escalation scheme, the sample size calculation assumes that dose level 1 will include 3 to 6 patients and dose level 2 will have 6 patients as shown in the Figure JJCC.1. This sample size was not based on a statistical power calculation.

### **5.3. Method of Assignment to Treatment**

Patients who meet all criteria for enrollment will be assigned to receive LY3039478 in this study. Before each patient's enrollment into the study, an eligibility check must be conducted between the investigational site and the Lilly clinical research personnel to confirm that each patient meets all enrollment criteria. Upon confirmation of eligibility, the sponsor will confirm the dose, identification number assignment, and cohort for each patient. No dose escalations (that is, to the next cohort) can occur without prior discussion and agreement with the responsible Lilly clinical research physician (CRP)/clinical research scientist (CRS).

If investigators have eligible patients who have consented concurrently, >3 patients may be entered at a particular dose level provided that accrual has not ceased due to excessive toxicity. This enrollment procedure is allowed because of the advanced disease state of this patient population and the screening involved in defining eligibility. This event should be approved by the sponsor following discussions with the investigators.

## 6. A Priori Statistical Methods

### 6.1. General Considerations

Statistical analysis of this study will be the responsibility of Lilly.

The interpretation of the study results will be the responsibility of the investigator with the Lilly CRP or CRS, pharmacokineticist, and statistician. The CRP or CRS and statistician will also be responsible for the appropriate conduct of an internal review for both the final study report and any study-related material to be authorized by Lilly for publication.

The analyses for this study will be descriptive, except for possible exploratory analysis as deemed appropriate. Data analyses will be provided by assigned dose level.

In general, continuous variables will be presented using the mean, standard deviation (SD), median, minimum, maximum and number of patients with an observation (n). For categorical variables, the population size (N), the number of events (n), the number of subjects with events (n) and the percentage of subjects with events are usually reported.

Any change to the data analysis methods described in the protocol will require an amendment ONLY if it changes a principal feature of the protocol. Any other change to the data analysis methods described in the protocol, and the justification for making the change, will be described in the clinical study report. Additional exploratory analyses of the data will be conducted as deemed appropriate and they will be planned in this SAP in advance.

The following data handling conventions will be used in the analysis.

Term	Definition or Rule
Relative Study Day	If assessment is on or after date of first dose then (date of assessment) – (date of first study drug dose) +1
	If assessment precedes first dose of drug then (date of assessment) – (date of first study drug dose)
	There is no study day 0. Study day 1 is the date of first dose and study day -1 is the day before the first dose.
Cycle Day	If assessment is on or after date of first dose in cycle then (date of assessment) – (date of first study drug dose in cycle) +1
	There is no cycle day 0. Cycle day 1 is the date of first dose in that cycle.
Duration of treatment	(Date of Day 1 of last cycle + 28 – Date of Day 1 of Cycle 1) / 7
Baseline	For change from baseline analyses, baseline value is defined as the last reported measure on or before the first dose date (prior to the dose administration), unless otherwise specified.
Entered	Patients who have signed the informed consent document directly or through their legally acceptable representatives.
Enrolled	Patients who have been assigned to study treatment and have received at least 1 dose of study treatment.
Efficacy Analyses Set	In principle, all patients who are enrolled in this study. A patient who are considered nonevaluable for the assessment of a dose level might be excluded from the efficacy analysis set. In this case, the nonevaluable condition will be specified before the data base lock.
Safety Analyses Set	All patients who have received at least 1 dose of study drug, regardless of whether they are deemed evaluable for the assessment of a dose level.

DLT Analyses Set	All patients who are deemed evaluable for DLT assessment. The evaluable patients must taken $\geq 75\%$ of the assigned dose in Cycle 1 (first 28 days) or experienced a DLT in Cycle 1 (first 28 days).
PK/PD Analyses Set	All patients who have received at least 1 dose of the study drug and have had sufficient postdose samples collected to allow estimation of PK parameters will form the PK/PD analyses set.
Screen Failures	Patients who have signed informed consent, do not meet eligibility criteria and are not enrolled.

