### **7.2.2.2. Dose Escalation Method**

In this study, dose escalation will be driven by safety using the 3+3 method. Dose escalation will proceed as follows:

Dose Level 1 (25 mg):

- 3 patients will be enrolled. If 1 out of 3 evaluable patients for DLT experience a DLT, 3 additional patients will be enrolled in the same dose level.
- If 0 out of 3, or 1 out of 6 evaluable patients for DLT experience a DLT, the dose will be escalated to Dose Level 2.
- If dose escalation is made based on 3 evaluable patients in Dose Level 1 and Dose Level 2 is judged as intolerable, an additional 3 patients will be enrolled in Dose Level 1 and tolerability of Dose Level 1 will be evaluated based on a total of 6 patients' data.

Dose Level 2 (50 mg):

- 6 patients will be enrolled. If  $\leq 1$  out of 6 evaluable patients for DLT experience a DLT, the dose will be judged as tolerable.

All dose levels:

- If 2 patients experience DLTs at any given dose, the sponsor will examine the safety data and consult with the SAC as needed. With the consultation, the sponsor and the primary investigator will decide if the dose is intolerable or additional patients will be enrolled to the same dose level.
- If  $\geq 3$  patients experience DLTs at any given dose, it will be judged that the dose is not tolerable for Japanese patients.

[figure not shown]
An evaluable patient for DLT is defined as a patient who takes  $\geq 75\%$  of the planned dose in Cycle 1 (first 28 days) or a patient who experiences DLT in Cycle 1 (first 28 days). A patient who takes  $<75\%$  in Cycle 1 due to reasons other than drug-related toxicity (for example, early discontinuation due to progressive disease) will be considered nonevaluable for DLT and replaced by a new patient. If a patient takes  $<75\%$  in Cycle 1 due to drug-related toxicities, the investigators and Lilly clinical research personnel will discuss whether the toxicities could be

deemed to be dose-limiting, and will consult with the SAC if needed. If it is not considered DLT, the patient is deemed to be nonevaluable for DLT and will be replaced by a new patient.

The reason for taking <75% of the planned dose needs to be documented appropriately and may be confirmed by the sponsor.

Dose escalation decisions will be made by agreement between the primary investigator and the sponsor, with a consultation with the SAC as needed. Additional patients may be enrolled at a specific dose level to characterize PK/PD or safety profile.

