### **7.6.1. *Evaluable Patients***

Patients who withdraw from the study before receiving study drug(s) will be replaced and will not be included in the safety or efficacy assessments. Safety analyses will be conducted on all patients who have received at least 1 dose of study drug, regardless of whether they are deemed evaluable for the assessment of a dose level.

Patients who are not evaluable for PK, but who complete Cycle 1, may be replaced upon consultation with the investigator and the Lilly CRP/CRS to ensure adequate PK data, unless accrual to that cohort has stopped due to a DLT.

Any patient who is discontinued from study treatment before completing Cycle 1 will be deemed nonevaluable for assessment of a dose level, unless they experience a DLT prior to withdrawal.

If the patient is noncompliant during Cycle 1 due to reasons other than drug-related toxicity, he or she will be considered nonevaluable and may be replaced.

Nonevaluable patients may be replaced to ensure that the required number of patients complete Cycle 1, unless accrual to that cohort has stopped due to a DLT.

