#### 10.1.1. Analysis Populations

Each analysis is done on a specific analysis population. The analysis populations are defined as follows:

- Efficacy Analyses Set: All patients who have received at least 1 dose of study drug and who are evaluable for the assessment of a dose level will form the efficacy analysis set. This population will be used in all efficacy reporting and analyses.
- Safety Analyses Set: All patients who have received at least 1 dose of study drug, regardless of whether they are deemed evaluable for the assessment of a dose level, will form the safety analysis set. This population will be used in all safety reporting and analyses.
- DLT Analyses Set: All patients in safety analysis set who are deemed evaluable for the assessment of DLT will form the DLT analyses set. The following patients will not be considered as evaluable for DLT:
  - Any patients who are discontinued from the study before completing 1 cycle of LY3039478 treatment will be deemed nonevaluable for assessment of a dose level, unless they experience a DLT prior to withdrawal.
  - If a patient is noncompliant during Cycle 1 due to reasons other than drug-related toxicity, he or she will be considered nonevaluable and may be replaced.
- PK/PD Analyses Set: All patients who have received at least 1 dose of the study drug and have had sufficient postdose samples collected to allow estimation of PK parameters will form the PK/PD analyses set. This population will be used in all PK/PD reporting and analyses.

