Tumor biopsy (optional)	Optional. Collected at baseline/screening and posttreatment tumor biopsy should be obtained (whenever clinically feasible) at Cycle 1, preferably 6 to 8 hours after Dose 10 (Day 22). Greater flexibility has been provided for the posttreatment tumor biopsy (between Doses 7 and 12, inclusive) compared to other Dose 10 visit assessments ( $\pm$ 3 days of planned visit) to enable radiographic guidance and access to appropriate medical specialists; however, if this flexibility is exercised and the posttreatment tumor biopsy is obtained on a day other than Cycle 1 Day 22 (Dose 10) visit, then a single PK sample should be obtained as close as possible (for example, $\pm$ 3 hours) to the time of the biopsy. Additional optional tumor biopsies may be performed at time of disease progression and if deemed necessary by the investigator. Tumor biopsy must be collected only if the investigator does not anticipate any significant bleeding post-treatment. If the investigator considers a high risk of significant bleeding, the procedure should be omitted.
Tumor marker (if applicable)	Optional. Conducted at local laboratory, if applicable.

Assessment	Comments
Radiological tumor assessment (CT/MRI)	Radiological assessment is performed at baseline (up to 28 days before the first dose but the assessment obtained prior to informed consent may be used as the baseline assessment provided they were performed within 28 days of Cycle 1 Day 1), then at the end of Cycle 2 (no more than 10 days prior to Day 1 of Cycle 3[inclusive]). If the start of Cycle 3 is delayed, then it is not necessary to perform the assessment again in the time window of 10 days prior to Day 1 of Cycle 3. After Cycle 4 (inclusive), radiological assessment is performed at Day 15 of every other cycle. Radiological assessment performed out of time window ( $\pm$ 3 days of planned date) due to logistical reasons or patient safety concerns may not be considered as a deviation but the investigator should make every effort to conduct as close to the time window as possible. For patients who discontinue study treatment without objectively measured progressive disease, the radiological tumor assessment is not required. If the result of assessment is available by 30- day follow-up visit, it should be reported.

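### The protocol and the SAP define the efficacy set differently, and dropping patients who progress in Cycle 1 raises the response rate whenever anyone responds

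*SAP*

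**What the plan says.** Protocol 10.1.1 builds the efficacy set from "All patients who have received at least 1 dose of study drug and who are evaluable for the assessment of a dose level" and applies it to all efficacy reporting. SAP 6.1 takes all enrolled patients, meaning those assigned and dosed, as the set in principle, and then allows an exception: "A patient who are considered nonevaluable for the assessment of a dose level might be excluded from the efficacy analysis set". It continues: "In this case, the nonevaluable condition will be specified before the data base lock".

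Evaluability for a dose level is defined for the tolerability decision. Protocol 7.6.1 states: "Any patient who is discontinued from study treatment before completing Cycle 1 will be deemed nonevaluable for assessment of a dose level", except where a DLT came first. Protocol 10.1.1 repeats this under the DLT set. Protocol 7.2.2.2 uses a different test, at least 75% of the planned Cycle 1 dose or a DLT. It names progression as an example of a reason for falling short, after which the patient is nonevaluable and replaced. For a patient below 75% because of drug-related toxicity it says: "If it is not considered DLT, the patient is deemed to be nonevaluable for DLT and will be replaced by a new patient".

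SAP 6.10.1 divides the overall response rate (ORR) by all patients in the efficacy set. It requires two determinations of response before progression, with repeat imaging at least 4 weeks after the first. SAP 6.3 says separately that response analyses include all patients with measurable disease. On reporting, SAP 6.1 states: "Data analyses will be provided by assigned dose level".

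**The concern.** One document makes the exclusion mandatory. The other makes it optional and leaves its condition open. Both are current text: SAP Version 3 was approved on 02-Apr-2019 and Protocol Amendment (b) on 12-Apr-2019. The SAP revision history does not mention the departure from the protocol. The same data can therefore give two response rates, and in an open-label study the choice can be made after responses are known.

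The protocol's rule also has a direction. A DLT-evaluability criterion suits a tolerability decision, where a patient who leaves early for progression carries little information. For a response rate, that patient is an observed treatment failure, and removing failures raises the rate.

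A second ambiguity concerns the denominator. Patients with nonmeasurable disease only are eligible (Protocol 6.1.1) and can be rated CR under Table 2 of Protocol Attachment 9. SAP 6.3 can be read as leaving them out of response analyses, while SAP 6.10.1 counts them if they are in the efficacy set.

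**Working it through.** **Planned size.** SAP 5.2 gives 3 to 6 patients at dose level 1 and 6 at dose level 2. 3 + 6 = 9 and 6 + 6 = 12, which reproduces the 9 to 12 in the protocol synopsis. No expected response rate or number of nonevaluable patients is stated.

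**Can a Cycle 1 progressor be a confirmed responder?** The first scheduled on-study scan is at the end of Cycle 2, at most 10 days before Cycle 3 Day 1 (Protocol Attachment 1).

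- Cycle 3 Day 1 = 28 + 28 + 1 = Day 57.
- Earliest scheduled scan = 57 − 10 = Day 47.
- Earliest confirmation = 47 + 28 = Day 75.
- Cycle 1 ends on Day 28.

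Even with unscheduled scans, two post-dose determinations 28 days apart cannot both come before progression within a 28-day cycle. Such a patient is a certain non-responder.

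**Effect on the rate.** Let m be the number of evaluable patients (held fixed by replacement), k the number of excluded Cycle 1 progressors and r the number of responders.

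- Protocol set: r/m.
- All dosed patients: r/(m + k).
- Ratio of the two: (m + k)/m, which exceeds 1 whenever k ≥ 1. If r = 0, both rates are zero.

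The values of r and k below are assumptions.

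| m | r | k | Evaluable only | All dosed | Difference (points) | Ratio |
|---|---|---|---|---|---|---|
| 6 | 1 | 1 | 1/6 = 16.7% | 1/7 = 14.3% | 2.4 | 1.17 |
| 6 | 1 | 2 | 1/6 = 16.7% | 1/8 = 12.5% | 4.2 | 1.33 |
| 6 | 1 | 3 | 1/6 = 16.7% | 1/9 = 11.1% | 5.6 | 1.50 |
| 6 | 2 | 1 | 2/6 = 33.3% | 2/7 = 28.6% | 4.8 | 1.17 |
| 6 | 2 | 3 | 2/6 = 33.3% | 2/9 = 22.2% | 11.1 | 1.50 |
| 12 | 1 | 1 | 1/12 = 8.3% | 1/13 = 7.7% | 0.6 | 1.08 |
| 12 | 1 | 2 | 1/12 = 8.3% | 1/14 = 7.1% | 1.2 | 1.17 |
| 12 | 1 | 3 | 1/12 = 8.3% | 1/15 = 6.7% | 1.7 | 1.25 |

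**Opposite direction.** A patient who is nonevaluable only because non-DLT toxicity kept the Cycle 1 dose below 75% may stay on treatment and respond. Excluding that patient could turn 2/13 = 15.4% into 1/12 = 8.3%. The upward direction is therefore certain for Cycle 1 progressors, not for every possible exclusion.

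**Scale.** The exact (Clopper-Pearson) 95% interval for 1/12 is 0.2% to 38.5%.

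**The case against.** The strongest objection is materiality. The study was not designed for a formal efficacy assessment, no hypothesis is tested, and the response rate feeds no dose decision. Analysis-set counts, discontinuation reasons and response listings are all planned, so a reader could recompute either rate. The absolute shifts are small beside the interval, and the counts are assumed. All of this stands and limits the severity. It does not settle which rate is reported for a stated secondary objective.

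The SAP default is already the all-dosed set, and an exclusion condition is needed only if an exclusion is used. That is a fair reading of SAP 6.1, but the option remains open until lock, and Protocol 10.1.1 still makes the exclusion mandatory. SAP 6.1 does allow changes from the protocol's analysis that leave its principal features intact, if they are justified in the study report. That permission does not supply the missing condition.

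Not every Cycle 1 progressor is nonevaluable under every rule. Someone who took at least 9 of the 12 scheduled doses (9/12 = 75%) and then stopped meets the 75% test in Protocol 7.2.2.2 but is nonevaluable under 7.6.1 and 10.1.1. Conversely, the low-dose toxicity case above rests on 7.2.2.2 and is not among the exclusions listed in 10.1.1. Both points are correct. They show that the exclusion criterion is itself unsettled, since 10.1.1 uses DLT evaluability and dose-level evaluability interchangeably.

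Finally, SAP 6.3 restricts the tumor-size analysis with the word only and does not use it for response, so its response sentence may be meant as a guarantee of inclusion. That reading is possible, which is why the point about measurable disease is one of clarity.

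**Conclusion.** The concern holds. The efficacy set is defined in two incompatible ways in current text. The protocol's version removes certain non-responders and raises the response rate whenever at least one patient responds and at least one Cycle 1 progressor is excluded. With 1 responder and 1 to 3 excluded patients, the relative inflation is 17% to 50% in a 6-patient cohort (2.4 to 5.6 points) and 8% to 25% with 12 evaluable patients (0.6 to 1.7 points). Because results are reported by dose level, the cohort figures are the relevant ones. The sizes rest on assumed counts and on replacement keeping the evaluable number fixed; the direction does not depend on the particular counts. The tolerability conclusion is unaffected. This should be corrected, but it does not threaten the primary objective.

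**What to change.** - In Protocol 10.1.1 and SAP 6.1, define the efficacy set as all patients who received at least one dose, and delete the exclusion of patients nonevaluable for a dose level.
- In SAP 6.10.1, state that patients with no post-baseline assessment are classed as not evaluable and count as non-responders in the ORR.
- In SAP 6.3, state that the ORR denominator is the full efficacy set and that the measurable-disease restriction applies only to change in tumor size.
- Report any evaluable-only or measurable-only rate as a labelled supplement.

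The cost is wording in two documents, including a protocol amendment, with no new data. The downside is a possibly lower headline rate: in the illustrations with 1 responder, 11.1% to 14.3% instead of 16.7% in a 6-patient cohort, and 6.7% to 7.7% instead of 8.3% overall.
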